**6.4.7 Doppler Echocardiography**

Color Doppler echocardiography (ECHO) will be conducted at a facility with experience for the subject’s age at Screening, Maintenance period (Visit 8), End of study (Visit 12), and Cardiac Follow-up (Visit 14). ECHO uses ultrasound technology to examine the heart or blood vessels. An ECHO uses high frequency sound waves to create an image of the heart while the use of Doppler technology allows determination of the speed and direction of blood flow by utilizing the Doppler effect. Predetermined standard guidelines on the proper evaluation of certain measurements, as well as abnormality thresholds, were constructed by the sponsor’s IPCAB prior to study initiation. These thresholds are provided in the below table:

Signs on ECHO indicative of potential Valvulopathy
 
 
• valve regurgitation (aortic or mitral)
 
• ≥ mild valve regurgitation (tricuspid, or pulmonary)
 
• Mean Mitral valve gradient ≥ 4 mmHg
 
• Mean Aortic valve gradient ≥ 15 mmHg
 
• Mean Tricuspid valve gradient ≥ 4mmHg
 
• Peak Pulmonary valve gradient ≥ 21mmHg
 
	
Normal Values for Children 2-18 years
 
 
• No regurgitation
 
• Mean Mitral valve gradient < 4 mmHg
 
• Mean Aortic valve gradient < 15 mmHg
 
• Mean Tricuspid valve gradient < 4mmHg
 
• Peak Pulmonary valve gradient < 21mmHg
 

-------------------------------------------------------------------------------------------------------------------------------------------------------------------------------------------------------------------------------------------------------------------------------------------------------------------------------------------------------------------------------------------------------------------------------	---------------------------------------------------------------------------------------------------------------------------------------------------------------------------------------------------------------------------------------------------------------------------------------------------------------------------------

**Signs on ECHO indicative of pulmonary hypertension**

- a. Tricuspid Regurgitation Jet velocity > 2.8 msec with or without the following findings OR  
b. One of the following findings in the absence of being able to measure Tricuspid Regurgitation Jet velocity:
- i. Change in right ventricle/left ventricle basal diameter ratio > 1.0
  - ii. Right ventricular acceleration time < 100 msec
  - iii. Dilatation of the inferior caval vein (diameter > 21 mm and < 50% inspiratory decrease) and/or right atrium
  - iv. Change in the geometry of the interventricular septum in systole (flattening) with left ventricular eccentricity index > 1.1 in systole and/or in diastole
  - v. Early diastolic pulmonary regurgitation velocity > 2.2 m/sec
  - vi. Tricuspid Annular Plane Systolic Excursion below 18 mm or below Z-score - 2

Results of ECHOs will be presented in a separate report from Biomedical Systems.

**6.4.8 Tanner Staging**

Tanner Staging will be assessed for subjects >7 years old during the study at baseline period (Visit 3) and End of study (Visit 12). Conceptually, pubertal maturation can be described in terms of sequence, timing, and tempo. Puberty consists of a series of predictable events, and the sequence of changes in secondary sexual characteristics has been categorized by several groups. The onset and progress of pubertal changes will be recorded on a 5 point scale for boys and girls separately. Boys are rated for genital development and pubic hair growth through stage I to stage V. Girls are rated for breast development and pubic hair growth through stage I to stage V.

The number and percentage of subjects in each Tanner Stage will be presented for all visits by treatment group separately for boys and girls overall and also broken out for the following age groups:

- >7years to <=11,
- >11years to <=15,
- >15years to <=18.

All Tanner staging data will be presented in the subject data listing.

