**STATISTICAL ANALYSIS PLAN**  
Zogenix International Limited  
ZX008 Study 1

Table	14.3.2.3	Listing of Discontinuations Due to AE
14.3.4 Summary of Laboratory Data		
Table	14.3.4.1	Laboratory parameters – Hematology– Safety Population
Table	14.3.4.2	Laboratory parameters – Biochemistry– Safety Population
Table	14.3.4.4	Laboratory parameters – Urinalysis – Safety Population
Table	14.3.4.4.1	Laboratory parameters – Urinalysis (Quantitative parameters) – Safety Population
Table	14.3.4.4.2	Laboratory parameters – Urinalysis (Categorical parameters) – Safety Population
Table	14.3.4.5	Laboratory parameters – Tests of growth and precocious puberty –Safety Population
Table	14.3.4.6	Laboratory parameters – Epilepsy genotype panel – descriptive statistics – Safety Population
14.4.1 Vital Signs		
Table	14.4.1.1	Vital signs parameters – Safety Population
14.4.4 Tanner Staging		
Table	14.4.4.1	Tanner staging by age group for Boys– Safety Population
Table	14.4.4.2	Tanner staging by age group for Girls– Safety Population
14.4.5 Columbia-Suicide Severity Rating Scale (C-SSRS)		
Table	14.4.5.1	Number of Patients with Suicidal Ideation, Suicidal Behavior, and Self-Injurious Behavior without Suicidal Intent Based on the C-SSRS – Safety Population
Table	14.4.5.2	Columbia Suicide Severity-Rating Scale (C-SSRS)- Shift Table of Changes in C-SSRS Categories During Treatment - Safety Population
14.4.6 Brief Rating Inventory of Executive Function- (BRIEF)		
Table	14.4.6.1	BRIEF-P – Scoring summary table by treatment group – Safety Population
Table	14.4.6.2	BRIEF – Scoring summary table by treatment group – Safety Population
16.1.9.2 Statistical Output		
Output	16.1.9.2.1	Output from Primary Efficacy Analysis
Output	16.1.9.2.2	Output from Secondary Efficacy Analyses
16.2 Subject data listing		
16.2.1 Subject disposition and discontinuation		
Listing	16.2.1.1	Subject completion/discontinuation
16.2.2 Protocol deviations		

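### Tanner staging is summarised only as stage counts at each visit, which show the net shift in stage but not how many children advanced

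*SAP*

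**What the plan says.** Section 6.4.8 of the Study 1 SAP has children over 7 years staged twice, at Visit 3 and at Visit 12. It describes the aim of the data collection as follows: "The onset and progress of pubertal changes will be recorded on a 5 point scale for boys and girls separately". Boys have a genital and a pubic hair rating; girls have a breast and a pubic hair rating.

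The planned summary is: "The number and percentage of subjects in each Tanner Stage will be presented for all visits by treatment group". This is done for each sex, once over all ages and again within three age bands (over 7 to 11, over 11 to 15, over 15 to 18). For individual data: "All Tanner staging data will be presented in the subject data listing".

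The Study 1 list of outputs (Appendix 1) contains two Tanner tables, 14.4.4.1 "Tanner staging by age group for Boys– Safety Population" and 14.4.4.2 "Tanner staging by age group for Girls– Safety Population", plus Listing 16.2.9.4. Section 10.10 of the Study 2 SAP carries the same rule, and its index adds only Japan versions of the two tables. Neither SAP plans a shift table, a change from baseline or a count of children who advance.

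**The concern.** Tanner stage is an ordinal rating taken twice on the same child. The natural question for a before-and-after rating is how many children moved up a stage in each arm. A table of stage counts at each visit does not use the pairing, so it does not answer that question directly.

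The plans treat comparable data differently elsewhere:

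- The neurological examination gets shift tables (Study 1 Section 6.4.4, Study 2 Section 10.9).
- The C-SSRS gets a shift table (Table 14.4.5.2 in both indexes).
- The growth and precocious puberty hormones get change from baseline (Study 1 Section 6.4.9, Study 2 Section 10.4).
- The Study 2 cardiovascular SAP (Section 2.3.2.2) counts subjects whose tricuspid or pulmonic regurgitation goes from normal or trace at baseline to at least mild at end of study.

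At stake is how readily a reader can compare pubertal progression between arms.

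**Working it through.** The plans state no figure for this point, so there is none to reproduce. The check is whether stage counts at two visits determine how many children advanced. The data below are constructed for the purpose and do not come from the documents.

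**Step 1: complete data.** Take ten children in one arm and sex, all staged at both visits on one rating. The planned table would show:

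| | Stage I | Stage II | Stage III |
|---|---|---|---|
| Visit 3 | 5 | 4 | 1 |
| Visit 12 | 4 | 4 | 2 |

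Three different histories produce exactly these rows:

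- One child goes I to III and nobody else moves: 1 advances.
- One child goes I to II and one goes II to III: 2 advance.
- Three go I to II, one goes II to III and two go II to I (possible with rating error): 4 advance, 2 regress.

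**Step 2: what the rows do fix.** Add up the stage numbers. Visit 3 gives 5×1 + 4×2 + 1×3 = 16. Visit 12 gives 4×1 + 4×2 + 2×3 = 18. The net movement is 18 − 16 = 2 steps. All three histories give 2: (+2), (+1 +1) and (+4 −2). With complete data the net shift is therefore determined; the number of children who advanced is not.

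**Step 3: one child not rated at Visit 12.** Start again from 5, 4, 1 and suppose the Visit 12 row is 4, 4, 1 with N = 9. This row arises in three ways:

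- The missing child was in stage I and nobody moved: 0 advance, net 0.
- The missing child was in stage II and one child went I to II: 1 advances, net +1.
- The missing child was in stage III, one child went I to II and one went II to III: 2 advance, net +2.

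The drop in N shows that a child is missing, but not which one. Once attrition and change occur together, the table does not fix even the net movement.

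**Step 4: how often Step 3 applies.** The Study 1 schedule (Table 1) puts Tanner staging in the EOS/ET column, and Section 6.1.6 treats the early termination visit as Visit 12, so early leavers are due a second rating. The Study 2 SAP (Section 6.4) gives Study 1 dropout as 9/119 = 7.56%, which is 9/3 = 3 per arm on average over all ages. Unpaired ratings should be few. A child who passes age 7 between the visits could also be rated only once. Section 6.4.8 has no rule for this, whereas the C-SSRS section (6.4.10) does cover a seventh birthday during the study.

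**Step 5: definition of the rows.** Each child has two ratings, but the summary does not say whether they are tabulated separately. Nor does it say that the age band is fixed at baseline, so a child who has a birthday at a band limit could change band between visits. The Study 2 SAP (Section 7.2) computes age at Study Day 1 for demographics; Section 10.10 does not say that this age defines the bands.

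**The case against.** The case for leaving the plan alone is substantial, and most of it stands.

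- **Overall counts exist.** A reader might infer that the counts come only within small age bands and are too thin to read. Section 6.4.8 also gives them overall for each sex.
- **Net movement is visible.** A reader might infer that an excess of progression in one arm could not be seen in the tables. Step 2 shows that, with complete data, a net excess would appear.
- **A single dropout can be recognised.** A reader might infer that one dropout looks the same as one advance. It does not: the plan gives numbers as well as percentages for every stage, so the total and the later-stage counts differ. The difficulty arises only when the two occur together, as in Step 3.
- **There is no contradiction.** The statement about onset and progress concerns what is recorded. Two ratings and a listing satisfy it, and shift tables for other scales create no obligation here.
- **Puberty is covered in other ways.** LH, FSH, testosterone, estradiol, prolactin and growth markers are summarised as change from baseline. Raised prolactin, galactorrhea and gynecomastia are adverse events of special interest. New, clinically meaningful findings on physical examination become adverse events. It would be wrong to say that a pubertal signal could be found only in listings.
- **Few changes are likely** in about 14 weeks.

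What is left is narrow. No planned table gives the number of children who advanced, either on each rating or among those staged at both visits.

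**Conclusion.** The point holds as a low-severity improvement. The planned tables show the net shift in stage when ratings are complete, but not how many children advanced. In the constructed example the same rows fit 1, 2 or 4 children advancing with complete data, and 0, 1 or 2 when one child is unrated at Visit 12. Those figures show that the counts do not identify the answer; they do not predict what the trial would find. The documents give no expected rate of stage advance, so no size of missed effect can be stated.

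The conclusion rests on the text of Sections 6.4.8 and 10.10 and on the two output lists. Individual data are kept in the listing, so nothing is lost, only left unsummarised. Efficacy inference is unaffected, and no test is planned on this scale.

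**What to change.** In Study 1 Section 6.4.8 and Study 2 Section 10.10, and in the corresponding output lists:

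- Add a Visit 3 to Visit 12/ET shift table for each rating (genital or breast, and pubic hair), by arm and sex, restricted to children staged at both visits. State the number staged at only one visit.
- Add the number and percentage per arm advancing at least one stage on either rating, pooled over age bands.
- Define the age band by age at baseline.
- Keep the by-visit stage counts as supporting output, and state that the two ratings are tabulated separately.

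The cost is one extra descriptive table from data already collected; no new assessment is needed.

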**6.4.9 Laboratory Parameters**

Laboratory safety parameters will be analyzed by a central laboratory using standard validated methods.

All laboratory safety data will be collected as per the schedule of assessments given in [Table 1](#).

The following continuous laboratory parameters will be analyzed:

- Hematology: hemoglobin, hematocrit, erythrocytes, erythrocyte mean corpuscular volume, leukocytes, neutrophils, lymphocytes, monocytes, eosinophils, basophils and platelets
- Blood Biochemistry: albumin (ALB), alkaline phosphatase (AP), alanine aminotransferase (ALT; SGPT), aspartate aminotransferase (AST; SGOT), blood urea nitrogen (BUN), calcium (Ca), carbon dioxide (CO2), chloride (Cl), creatinine, creatine

kinase, gamma-glutamyl transferase (GGT), globulin, glucose, lactate dehydrogenase (LDH), phosphorus, potassium (K), sodium (Na), thyroid function, thyroid stimulating hormone (TSH), total bilirubin, direct bilirubin, total cholesterol, total protein, triglycerides, uric acid.

- Tests of growth and precocious puberty: Growth hormone (GH), insulin-like growth factor-1 (IGF-1, low sensitivity), prolactin, Luteinizing Hormone (LH), Follicle Stimulating Hormone (FSH), testosterone, estradiol
- Coagulation: Prothrombin time (PT)/International normalized ratio (INR), activated partial thromboplastin time (PTT)
- Whole blood cannabidiol
- Urinalysis: analysis for pH, glucose, ketones, nitrite, protein, bilirubin, urobilinogen, leukocyte esterase, and occult blood. Microscopic analysis will be performed for blood, all cell types, and casts.
- Urine pregnancy test: Urine pregnancy testing will be performed in female subjects of childbearing potential.
- Urine THC panel

Observed continuous laboratory data will be descriptively summarized by type of laboratory test/parameter by treatment group. Changes from baseline will also be presented for all continuous laboratory parameters by treatment group over time.

Categorical laboratory parameters will be summarized by presenting the number and % of subjects by visit and by treatment arm.

All laboratory values (including invalid values, reference ranges, and possible flags (low, high,)) will be presented in the subject data listings.

A listing of subjects with Potentially Clinically Significant (Extreme) laboratory results will be provided.

#### **6.4.10 Columbia-Suicide Severity Rating Scale**

Columbia-Suicide Severity Rating Scale data will be collected as per at screening visit (Visit 1), at randomization (visit 3), Titration period (at visit 6), maintenance period (at Visit 8 and 10) and at End of study visit (Visit 12).

Subjects who are younger than 7 years chronologically, or who are judged by the investigator not to have the mental capacity to understand the questions as specified on the C-SSRS, will not complete the rating. The investigator should use his/her judgment to substitute intellectually-appropriate questions to probe the tendency for self-harm.

If a subject with the intellectual capacity to complete the C-SSRS has their 7th birthday during the study, use of the C-SSRS should be initiated at subsequent visits.

All individual subject C-SSRS data will be listed.

#### **Suicidal Ideation:**

The following outcomes are C-SSRS categories for suicidal ideation and have binary responses (yes/no):

Category	Outcome Description
1	Wish to be dead
2	Non-specific active suicidal thoughts
3	Active suicidal ideation with any methods (not plan) without intent to act
4	Active suicidal ideation with some intent to act, without specific plan
5	Active suicidal ideation with specific plan and intent

Suicidal ideation is assessed as a “yes” answer at any time during the T + M period to any one of the five questions (1-5) above. The number and percentage of subjects with suicidal ideation will be presented, as well as the number and percentage having a “yes” response to each category (1-5) at least once during the T + M period. The denominator will be the number of subjects completing the C-SSRS at least once during the T + M Treatment period.

**Suicidal Behavior:**

The following outcomes are C-SSRS categories for suicidal behavior and have binary responses (yes/no):

Category	Outcome Description
6	Preparatory acts or behavior
7	Aborted attempt
8	Interrupted attempt
9	Actual attempt (non-fatal)
10	Completed suicide

Suicidal behavior is assessed as a “yes” answer at any time during the T + M period to any one of the five questions (6-10) above. The number and percentage of subjects who had suicidal behavior, as well as the number and percentage having a “yes” response to each category (6-10) at least once during the T + M period. The denominator will be the number of subjects completing the C-SSRS at least once during the T + M period.

**Suicidal Ideation or Behavior:**

An overall composite will be provided similar to the suicidal ideation and behavior endpoints, but will instead count a subject if any of the C-SSRS questions 1 through 10 are marked as ‘yes’ anything during the T+M period.

**Self-injurious behavior without suicidal intent:**

---

The number and percentage of subjects having reported anytime during the T+M period experiencing a 'Self-injurious behavior without suicidal intent' event (Question 11) will be provided.

#### **6.4.11 Brief Rating Inventory of Executive Function (BRIEF and BRIEF-P)**

The Behavior Rating Inventory of Executive Function (BRIEF™) and its preschool version, BRIEF-P, are standardized, validated rating scales to measure executive function in children within the home and school environments that will be assessed by the parent according to the schedule in Table 1 (i.e. at Randomization (Visit 3), at Maintenance period (Visit 8) and at End of study visit (Visit 12)).

The BRIEF measures multiple aspects of executive functioning; scales include Inhibit, Shift, Emotional Control, Initiate, Working Memory, Plan/Organize, Organization of Materials and Monitor.

The original BRIEF was the basis for the development of the BRIEF-P. The BRIEF-P Rating Form consists of 63 items that measure various aspects of executive functioning: Inhibit, Shift, Emotional Control, Working Memory, and Plan/Organize.

For the BRIEF and the BRIEF-P, mean scores at Baseline, End of Study/ET and mean change from baseline to End of Study/ET, and descriptive statistics will be presented by treatment group for the Safety population (SAF).

### **6.5 PK/PD ANALYSIS**

The bioanalytical methods for the determination of individual plasma concentrations of fenfluramine and its metabolite (norfenfluramine) will be reported together with the plasma concentration results in separate bioanalytical reports. These bioanalytical reports will be issued as a separate report.

### **6.6 ANALYSIS OF OTHER ASSESSMENTS**

Not applicable

### **6.7 INTERIM ANALYSIS**

No formal interim analysis is planned for Study 1. However, the cohort of subjects that comprise Study 1 are subsets of subjects from Study 1501 and Study 1502.

Unblinding for Study 1 will not occur until data cleaning is completed and all decisions regarding protocol deviations warranting exclusion from the per protocol population have been made. Personnel from the sponsor or any designee who become unblinded for the purposes of data cleaning and database lock for Study 1 will not participate in decision-making regarding subjects' data for Study 2 (the remainder of subjects entering Study 1501 or Study 1502) to avoid any real or apparent bias in such decisions.

### **6.8 INDEPENDENT DATA SAFETY MONITORING COMMITTEE**

The IDSMC is an independent advisory body that monitors participant safety, data quality and progress of all clinical trials. The IDSMC charter will outline the roles and responsibilities of the committee and guide its operations and frequency of meetings. The IDSMC will consist of

individuals external to the sponsor who have relevant clinical trial expertise and experience in safety assessment.

At regularly defined intervals, the IDSMC will convene to review and monitor study progress, AEs and SAEs, other measures of safety such as ECGs or ECHOs, and efficacy data as dictated by the charter.

The IDSMC will:

- Be responsible for providing recommendations to the sponsor surrounding study conduct matters that affect safety.
- Review safety data at ad hoc time points and identify if significant safety concerns arise during the study.
- Review pharmacokinetic data and any other data that may affect subject continuation.
- Make recommendations regarding the continuation, suspension, or termination of the study.

The list of tables, listings, and figures will be provided to the IDSMC as per IDSMC charter.

#### **6.9 CHANGES TO METHODS PLANNED IN THE PROTOCOL**

- The 1501 and 1502 protocols set a target that 40% of enrolled subjects to be less than 6 years old, but candidate subjects have been older than expected. Consequently, the enrollment target has been revised to ensure that at least 25% of subjects are less than 6 years old.
- Protocols 1501 and 1502 state that efficacy and safety endpoints will be repeated separately for the titration and maintenance periods, however this is not planned to be conducted –Data from the T+M Period will be summarized and analyzed for all endpoints, and separate analyses of titration or maintenance periods will be generated only for selected endpoints.
- Protocols 1501 and 1502 state that analyses of safety data will be presented by treatment actually received. However, safety data will be presented by randomized treatment group except where noted otherwise.
- Protocols 1501 and 1502 provide sample size calculations to support a total study sample of 105 subjects, 35 per treatment group. A revised sample size calculation has increased the sample size to 40 subjects per treatment group, for a total of approximately 120 subjects.
- Protocols 1501 and 1502 state that a sensitivity analysis for the primary efficacy endpoint will be conducted by adding a factor indicating whether a subject had a change in prescribed dose or type of concomitant AED medication during the T+M Period, however this is not planned to be conducted. Instead it is planned to compare the treatment groups with respect to the proportion of subjects who changed dose and/or type of AED concomitant medication during the T+M Period.
- Protocols 1501 and 1502 state that the longest interval between convulsive seizures will be analyzed using a log-rank test. However, further considerations of this endpoint suggest that while the first seizure-free interval may be subject to independent censoring, the second and later seizure-free intervals are subject to dependent censoring. Moreover, the last seizure-free interval is subject to intercept sampling, hence a longer seizure-free interval is more likely to be censored. Finally, the number of seizures or seizure-free

intervals is informative about the underlying distribution, as subjects at a higher risk of experiencing recurrent events are likely to have shorter and hence more seizure-free intervals during the 84 day treatment period. Thus, a simple analysis comparing medians of the largest seizure free intervals was proposed.

- Responder analyses – Protocols 1501 and 1502 include a  $\geq 40\%$  response analysis as one of the key secondary endpoints. It was decided to not include this endpoint.
- An analysis of the percentage of subjects who achieve a 25% reduction in seizures was added. The number of subjects whose seizures worsen during the study will be included, along with the percentage of worsening.
- The Protocol states that the BRIEF rating scale will be used to evaluate cognition in children aged 2-18. The BRIEF-P will be used for children aged 2-4, and the BRIEF will evaluate children aged 5-18.
- Interim analysis – Protocols 1501 and 1502 do not delineate an interim analysis. However, this Study 1 Analysis Plan is a pooled analysis of data from the first 120 subjects to be randomized into studies 1501 and 1502, in order to assess the benefit and risk at an earlier timepoint than fully recruiting each trial independently. Both studies will continue to enroll, and the remaining approximately 120 subjects will be analyzed as Study 2, under a separate analysis plan.

